4.2.2. Other Secondary Objectives

These are prespecified objectives that will not be adjusted for multiplicity.

Objective	Endpoint
To compare the efficacy of baricitinib 1-mg QD or 2-mg QD to placebo in AD during the 16-week, double-blind, placebo-controlled period as measured by improvement in signs and symptoms of AD	
 Proportion of patients achieving Investigator's Global Assessment (IGA) of 0 or 1 with a ≥ 2-point improvement at Week 4 Proportion of patients achieving 50% improvement from baseline using the Eczema Area and Severity Index score (EASI50) at Week 16 Proportion of patients achieving IGA of 0 at Week 16 Mean change from baseline in SCORing Atopic Dermatitis (SCORAD) at Week 16 Proportion of patients achieving SCORAD90 at Week 16 Mean change from baseline in body surface area affected at Week 16 Proportion of patients developing skin infections requiring antibiotic treatment by Week 16
To compare the efficacy of baricitinib 1-mg QD or 2-mg QD to placebo in AD during the 16-week, double-blind, placebo-controlled treatment period as assessed by patient-reported outcome/quality of life (QoL) measures	
 Mean percent change from baseline in Itch Numerical Rating Scale (NRS) at 1 week and 16 weeks Mean change from baseline in Itch NRS at 4 weeks and 16 weeks Mean change from baseline in the total score of the Patient-Oriented Eczema Measure (POEM) at Week 16 Mean change in Patient Global Impression of Severity (PGI-S-AD) scores at Week 16 Mean change from baseline in the Hospital Anxiety Depression Scale (HADS) at Week 16 Mean change in Dermatology Life Quality Index (DLQI) scores at Week 16 Mean change in Work Productivity and Activity Impairment: Atopic Dermatitis (WPAI-AD) scores at Week 16 Mean change in European Quality of Life-5 Dimensions-5 Levels (EQ-5D-5L) scores at Week 16

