		Percentage of absenteeism	Percent work time missed due to problem: $(Q2/(Q2 + Q4)) * 100$	If Q2 or Q4 is missing, then missing.
		Change from baseline in absenteeism	Change from baseline: observed absenteeism – baseline absenteeism	Missing if baseline or observed value is missing.
		Percentage of presenteeism	Percent impairment (reduced productivity while at work) while working due to problem: $(Q5/10) * 100$	If Q5 is missing, then missing.
		Change from baseline in presenteeism	Change from baseline: observed presenteeism – baseline absenteeism	Missing if baseline or observed value is missing.
		Overall work impairment	Percent overall work impairment (combines absenteeism and presenteeism) due to problem: $(Q2/(Q2+Q4) + [(1 - Q2/(Q2+Q4)) * (Q5/10)]) * 100$	If Q2, Q4, or Q5 is missing, then missing.
		Change from baseline in work impairment	Change from baseline: observed work impairment – baseline work impairment	Missing if baseline or observed value is missing.

Description and Derivation of Health Outcomes and Quality-of-Life Measures

Measure	Description	Variable	Derivation/Comment	Imputation Approach if with Missing Components
Work Productivity and Activity Impairment: Atopic Dermatitis (WPAI-AD)	
The WPAI-AD records impairment due to AD during the past 7 days. The WPAI-AD consists of 6 items grouped into 4 domains: absenteeism (work time missed), presenteeism (impairment at work/reduced on-the-job effectiveness), work productivity loss (overall work impairment/absenteeism plus presenteeism), and activity impairment. Scores are calculated as impairment percentages (Reilly et al. 1993), with higher scores indicating greater impairment and less productivity.
	
Percentage of impairment in activities
 
Change from baseline in impairment in activities
	
Percent activity impairment (performed outside of work) due to problem: $(Q6/10)*100$
 
Change from baseline: observed impairment in activities – baseline impairment in activities
	
If Q6 is missing, then missing.
 
Missing if baseline or observed value is missing.

Description and Derivation of Health Outcomes and Quality-of-Life Measures

Measure	Description	Variable	Derivation / Comment	Imputation Approach if with Missing Components

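### The missing-data rule for WPAI-AD overall work impairment has no exception for patients who worked no hours, where the plan's own formula gives 100% without Q5

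*SAP*

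**What the plan says.** SAP Section 4.2.2 lists, among the other secondary objectives not adjusted for multiplicity, "Mean change in Work Productivity and Activity Impairment: Atopic Dermatitis (WPAI-AD) scores at Week 16". Table JAIW.6.7 (Section 6.12) analyses four WPAI-AD scores at Week 16: absenteeism, presenteeism, overall work impairment and activity impairment. Each is analysed by MMRM, with ANCOVA on mLOCF data as sensitivity analysis, both under the primary censoring rule.

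Table JAIW.6.6 gives the derivations and the rules for missing components:

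- Absenteeism, "Percent work time missed due to problem", is Q2/(Q2 + Q4) × 100. Rule: "If Q2 or Q4 is missing, then missing".
- Presenteeism, "Percent impairment (reduced productivity while at work) while working due to problem", is (Q5/10) × 100. Rule: "If Q5 is missing, then missing".
- Overall work impairment, "Percent overall work impairment (combines absenteeism and presenteeism) due to problem", is (Q2/(Q2 + Q4) + [(1 − Q2/(Q2 + Q4)) × (Q5/10)]) × 100. Rule: "If Q2, Q4, or Q5 is missing, then missing".
- Its change score is "Change from baseline: observed work impairment – baseline work impairment", and is missing if either value is missing.

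Section 6.2.5 adds that a missing baseline is not imputed.

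**The concern.** Q5 rates productivity while at work. An employed patient who missed the whole recall week because of AD has no working time to rate and may well leave Q5 blank. The rule would then turn that patient's overall work impairment into a missing value, although the formula fixes it at 100%, the worst score possible.

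The table would also contradict itself for that patient. Absenteeism would be recorded as 100%, while overall impairment, which by construction cannot be lower than absenteeism, would be reported as unknown.

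What is at stake differs by visit. At Week 16 a score would be missing because of its own value. The MMRM assumes missingness at random (Section 6.4.2), so it does not address this. mLOCF (Section 6.4.3) would put in an earlier postbaseline value, which can only be equal to 100 or milder. Both analyses use the same derivation, so the sensitivity analysis would not expose the problem. At baseline, the most impaired workers would leave the change analysis.

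**Working it through.** **Inputs.** The formulas and missing rules are those of Table JAIW.6.6. The meanings of Q2 (time missed) and Q4 (time worked) are read from the absenteeism formula. The plan states no figure on this point, so there is none to reproduce first.

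**Step 1: the formula at Q4 = 0, Q2 > 0.** Write A = Q2/(Q2 + Q4). Overall impairment is (A + (1 − A) × Q5/10) × 100. With Q4 = 0, A = Q2/Q2 = 1, so the score is (1 + 0 × Q5/10) × 100 = 100. Evaluated for Q2 = 1, 8, 20 and 40 with Q5 = 0, 5 and 10, the result is 100 in all twelve cases. Q5 carries no weight.

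**Step 2: the rule as written.** For Q2 = 40, Q4 = 0 and Q5 blank, the score is missing. Absenteeism for the same patient is 40/40 × 100 = 100.

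**Step 3: where the rule is sound.** With Q4 > 0 the score does need Q5:

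| Q2 | Q4 | Q5 = 0 | Q5 = 5 | Q5 = 10 |
|---|---|---|---|---|
| 32 | 8 | 80 | 90 | 100 |
| 20 | 20 | 50 | 75 | 100 |

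With Q2 = Q4 = 0, A is 0/0 and the score is undefined. An exception must therefore require Q2 > 0.

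**Step 4: can Q5 be blank?** The SAP gives no skip pattern. Two features make a blank plausible. Q5 refers to impairment while working. The WPAI-AD also has item-level missing rules, one of them for Q5 alone, whereas for EASI, HADS and DLQI Table JAIW.6.4 or 6.6 says that incomplete forms cannot be stored. This remains an assumption.

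**Step 5: illustrative size.** The SAP gives neither the share of such patients nor the mean score, so both are assumed. If a share f of an arm's employed patients score 100 and are left out, and the others average m, the arm's observed mean falls by f × (100 − m) points:

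| f | m = 20 | m = 30 | m = 40 |
|---|---|---|---|
| 1% | 0.8 | 0.7 | 0.6 |
| 3% | 2.4 | 2.1 | 1.8 |
| 5% | 4.0 | 3.5 | 3.0 |
| 10% | 8.0 | 7.0 | 6.0 |

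Between arms, only the difference in f matters when m is equal. Take m = 30 in both arms. With 5% on placebo and 1% on baricitinib, the full means are 0.95 × 30 + 5 = 33.5 and 0.99 × 30 + 1 = 30.7. A difference of 2.8 points disappears when these patients are left out. With 2% and 1%, the means are 31.4 and 30.7, and 0.7 points disappear. These are raw means of the available scores at one visit, not results of the planned MMRM on change from baseline.

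**The case against.** The strongest reply is that harm requires a blank Q5, and nothing in the SAP says that it is blank. If such patients answer Q5, even with 0, they score 100 and nothing is lost. That stands, and it makes the point conditional. It does not count against the exception, which would then change no value.

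A reader might infer more than the documents support:

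- **That the patient drops out of the WPAI-AD endpoint.** A postbaseline blank loses one visit's overall score. Any other visits stay in the MMRM, and mLOCF uses any earlier postbaseline value. Absenteeism is kept at 100%, and activity impairment needs only Q6. Exclusion from the overall-impairment change analysis requires a missing baseline or no usable postbaseline score.
- **That the baseline loss biases the treatment comparison.** Baseline is taken on or before first dose (Section 6.2.3), so the loss cannot depend on treatment.
- **That the MMRM fills in mild values.** It imputes nothing explicitly. It uses the patient's other visits through their correlation, so a severely impaired patient is not simply treated as average.
- **That the illustrated points measure the bias.** Their inputs are assumed. The primary censoring rule (Section 6.4) already removes data after rescue or permanent drug discontinuation, which may take out some of the same patients at Week 16.

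It is also fair to object that a change now comes after unblinding. Section 6.2.1 reports the Week 16 lock as executed, and Table JAIW.6.7 analyses WPAI-AD at Week 16 only. That bears on how the change is reported, not on whether the rule is right.

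**Conclusion.** The point holds as a minor, conditional defect. It is certain, from the plan's own formula, that overall work impairment equals 100% when Q2 > 0 and Q4 = 0, and that the missing rule makes no exception for this case. It is assumed that Q5 is blank for at least some of these patients.

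Given that assumption, missingness at Week 16 depends on the outcome, and the loss favours whichever arm has more full-week absence. At baseline the loss reduces numbers and narrows the analysed population.

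The reach is one of four WPAI-AD scores, in employed patients, within an endpoint outside the multiplicity procedure. Primary and key secondary results are untouched. The size cannot be derived from the SAP. Under the assumed shares of 1% to 10% and means of 20 to 40, one arm's observed mean would shift by 0.6 to 8.0 points. Without a standard deviation in the plan, whether that is material cannot be judged.

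**What to change.** In Table JAIW.6.6, replace the missing rule for overall work impairment with: *If Q2 > 0 and Q4 = 0, overall work impairment = 100 regardless of Q5; otherwise missing if Q2, Q4 or Q5 is missing.* Apply it at baseline and postbaseline. Leave presenteeism missing in that case, because there is no working time to rate.

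Before rerunning, count the records with Q2 > 0, Q4 = 0 and Q5 blank, by arm and visit. If there are none, the change has no effect.

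As the Week 16 lock has been executed, report the result as a documented re-derivation made after unblinding, beside the analysis under the rule as written. The cost is one line of plan wording, a small amount of programming and that disclosure. No new data are needed.

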6.13. Bioanalytical and Pharmacokinetic/Pharmacodynamic Methods

No pharmacokinetic analyses are planned for this study.

6.14. Safety Analyses

The general methods used to summarize safety data, including the definition of baseline value, are described in Section 6.2.

Safety analyses will include data from , unless otherwise stated, and patients will be analyzed according to the investigational product to which they were randomized at Week 0 (Visit 2). Safety analyses will use the safety population defined in Section 6.2.2.

By-visit summaries will include planned on-treatment visits. For tables that summarize events (such as AEs, categorical lab abnormalities, shift to maximum severity), post-last dose follow-up data will be included. Follow-up data is defined as all data occurring up to 30 days (planned maximum follow-up time) after last dose of treatment including rescue, regardless of study period. Listings will include all safety data.

For the 16-week interim lock, all safety data up to the Week 16 visit and at time of the interim lock were included in the safety analysis. Safety data from patients who permanently discontinued study drug prior to time of the interim lock will be included in the interim lock safety analysis up to 30 days post-last dose of the study drug.

For the final DBL, safety data from the Week 16 visit date up to the end of the study will be included in the safety analysis. Safety data from patients who permanently discontinued study drug will be included in the safety analysis up to 30 days post-last dose of the study drug.

The following will be analyzed for the final DBL, based on Week 16 Responders:

- summary of study drug exposure
- overview of adverse events
- overview of infections
- summary of temporary interruptions of study drug
- summary of treatment-emergent adverse events
- serious adverse events, summary and listing, and
- adverse events leading to permanent discontinuation of study drug, summary and listing.

6.14.1. Extent of Exposure

Duration of exposure (in days) will be calculated as follows:

- Duration of exposure to investigational product (including exposure after the initiation of rescue therapy): *date of last dose of study drug including rescue – date of first dose of study drug +1.*

Last dose of study drug including rescue is calculated as last date on study drug. See the compound-level safety standards for more details.

Total patient-years (PY) of exposure to study drug will be reported for each treatment group for overall duration of exposure. Descriptive statistics will be provided for patient-days of exposure and the frequency of patients falling into different exposure ranges in addition to cumulative exposures will be summarized.

Exposure ranges will be reported in days using the following:

- ≥ 28 days, ≥ 56 days, ≥ 84 days, ≥ 112 days, ≥ 196 days, ≥ 364 days, ≥ 532 days, and ≥ 728 days
- >0 to <28 days, ≥ 28 days to <56 days, ≥ 56 days to <84 days, ≥ 84 days to <112 days, ≥ 112 days to <196 days, ≥ 196 days to <364 days, ≥ 364 days to <532 days, ≥ 532 days to 728 days, and ≥ 728 days

The exposure ranges will be redefined if very few patients are observed in a range.

The exposure ranges for the 16-week interim lock will be up to 112 days and including any exposure greater or equal to 112 days.

The exposure ranges for the final DBL will start from 112 days up to 728 days.

Overall exposure will be summarized in total PY, which is calculated according to the following formula:

$$\text{Exposure in PY (PYE)} = \frac{\text{sum of duration of exposure in days (for all patients in treatment group)}}{365.25}$$

6.14.2. Adverse Events

Adverse events are recorded in the eCRFs. Each AE will be coded to System Organ Class (SOC) and preferred term (PT) using the Medical Dictionary for Regulatory Activities (MedDRA) version that is current at the time of database lock. Severity of AEs is recorded as mild, moderate, or severe.

A TEAE is defined as an event that either first occurred or worsened in severity after the first dose of study treatment and on or prior to the last visit date during the analysis period. The analysis period is defined as the treatment period plus up to 30 days off-drug follow-up time.

A TEAE defined for the final DBL (Week 16 to end of study) is defined as an event that either first occurred or worsened in severity after the Week 16 visit date and on or prior to the last visit date during the analysis period. The analysis period is defined as the treatment period from the Week 16 visit date plus up to 30 days off-drug follow-up time. The baseline severity is defined as the most severity in the baseline period that is between the first dose date and the Week 16 visit date.

Adverse events are classified based upon the MedDRA PT. The MedDRA Lowest Level Term (LLT) will be used in defining which events are treatment-emergent. The maximum severity for each LLT during the baseline period up to first dose of the study medication will be used as baseline. If an event with missing severity is preexisting during the baseline period, and persists during the treatment period, then the baseline severity will be considered mild for determining treatment emergence (ie, the event is treatment-emergent if the severity is coded moderate or severe postbaseline and not treatment-emergent if the severity is coded mild postbaseline). If an event occurring postbaseline has a missing severity rating, then the event is considered treatment-emergent, unless the baseline rating is severe, in which case the event is not treatment-emergent. The day and time for events where onset is on the day of the first dose of study

treatment will both be used to distinguish between pretreatment and posttreatment in order to derive treatment emergence. Should there be insufficient data for AE start date to make this comparison (eg, the AE start year is the same as the treatment start year, but the AE start month and day are missing), the AE will be considered treatment-emergent.

In general, summaries will include the number of patients in the safety population (N), frequency of patients experiencing the event (n), and relative frequency (that is, percentage; $n/N*100$). For any events that are gender-specific based on the displayed PT, the denominator used to compute the percentage will only include patients from the given gender.

In an overview table, the number and percentage of patients in the safety population who experienced death, an SAE, any TEAE, discontinuation from the study due to an AE, permanent discontinuation from study drug due to an AE, or a severe TEAE will be summarized by treatment group.

The number and percentage of patients with TEAEs will be summarized by treatment group in 2 formats:

- by MedDRA PT nested within SOC with decreasing frequency in SOC, and events ordered within each SOC by decreasing frequency in the baricitinib 2-mg group for the final DBL;
- by MedDRA PT with events ordered by decreasing frequency in the baricitinib 2-mg group.

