5. Study Design

Study I4V-MC-JAIW (JAIW) is a multicenter, randomized, double-blind, placebo-controlled, parallel-group, outpatient Phase 3 study evaluating the efficacy and safety of baricitinib 1-mg QD and 2-mg QD as compared to placebo in adult patients with moderate to severe AD. The study is divided into 3 periods: a 5-week Screening Period, a 104-week Double-Blinded Treatment Period, and a 4-week Post-Treatment Follow-Up Period.

Approximately 450 patients aged ≥ 18 years who have responded inadequately to or who are intolerant of topical therapy will be randomized at a 1:1:1 ratio to receive placebo QD, baricitinib 1-mg QD, or baricitinib 2-mg QD (approximately 150 patients per group). Patients will be stratified at randomization according to disease severity (IGA 3 versus 4).

The primary and key secondary endpoints are assessed prior to or at Visit 8 (Week 16). At Week 16 those patients who met IGA 0 or 1 and who have not required rescue therapy prior to Week 16 will be allowed to continue in this study. All other patients will be discontinued from this study and may be eligible to enroll in a separate open-label study (Study JAIX). Patients experiencing worsening in disease severity resulting in an IGA score of ≥ 3 after Week 16 of Study JAIW will also have to be discontinued from this study and may be eligible to enroll in the open-label Study JAIX. Patients who complete Week 104 (Visit 15) will have the option to transition to open-label Study JAIX, if eligibility criteria are met regardless of responder status, or continue to the post-treatment follow-up.

Figure JAIW.5.1 illustrates the study design.

Abbreviations: AD = atopic dermatitis; QD = once daily; V = visit; W = week.

- ^a At Week 16, all patients who achieve an IGA 0 or 1 and who have not required rescue therapy before Week 16 will be allowed to continue in this study. All other patients will be discontinued from this study and may be eligible to enroll in the separate open-label Study JAIX.
- ^b Patients who complete this study will be eligible for assessment to enroll in open-label Study JAIX.
- ^c Occurs approximately 28 days after the last dose of investigational product.

Figure JAIW.5.1. Illustration of study design for I4V-MC-JAIW.

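### Both TEAE definitions stop at the last visit date, so an event after the last attended visit but within 30 days of last dose is not a TEAE, although Section 6.14 includes it

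*SAP*

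**What the plan says.** Section 6.14 sets the general rule for safety tables: "For tables that summarize events (such as AEs, categorical lab abnormalities, shift to maximum severity), post-last dose follow-up data will be included". It then gives the window: "Follow-up data is defined as all data occurring up to 30 days (planned maximum follow-up time) after last dose of treatment including rescue", and adds that this applies whatever the study period. No visit has to take place. For both the Week 16 interim lock and the final lock, the section repeats that patients who permanently stopped study drug contribute safety data to 30 days after their last dose.

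Section 6.14.2 gives adverse events the same period: "The analysis period is defined as the treatment period plus up to 30 days off-drug follow-up time". Its TEAE definition also imposes a second limit. The event must be new or have "worsened in severity after the first dose of study treatment and on or prior to the last visit date during the analysis period". In the final-lock definition, which starts at Week 16, the limit is repeated: the event must be new or have "worsened in severity after the Week 16 visit date and on or prior to the last visit date during the analysis period".

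A footnote to Figure JAIW.5.1 (Section 5) gives the timing of the follow-up visit: "Occurs approximately 28 days after the last dose of investigational product".

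**The concern.** The two sections close the window at different dates. One uses a fixed number of days after last dose. The other uses the last visit the patient attended inside that period, which can come earlier. An event between the two dates is follow-up data under Section 6.14 and lies within the analysis period of Section 6.14.2, but it fails the TEAE definition.

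The patients concerned are those who have an event after a visit and do not come back. An event reported at the next visit is counted. An event that keeps the patient from returning may not be, even if it began on drug. The outputs exposed are those conditioned on TEAE status: the any-TEAE and severe-TEAE rows of the overview, the TEAE tables by preferred term, and the infection summaries built on TEAEs (Section 6.14.5.6). The same overview table also counts deaths, SAEs and discontinuations due to an AE, with no TEAE condition. One patient could therefore appear as an SAE or a discontinuation and be absent from the TEAE row.

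**Working it through.** There is no stated figure to reproduce. The check compares the rules and then does date arithmetic.

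**Are the rules really different?**

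| Place in SAP | End of window | Visit required? |
|---|---|---|
| 6.14, event tables | last dose + 30 days | no |
| 6.14.2, analysis period | treatment + up to 30 days off drug | no |
| 6.14.2, TEAE (both definitions) | last visit date within that period | yes |
| 6.14.3 and 6.14.4, categorical laboratory and vital-sign analyses | treatment + up to 30 days off drug | no |

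Only the TEAE definitions carry the visit limit. Nothing in the SAP says that the last visit date means the end of the 30-day window, and nothing covers patients with no later visit.

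**How long is the uncovered interval?** Uncovered days = (last dose + 30) − (last visit date within the analysis period). With last dose as day 0:

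- follow-up visit on day +28: 30 − 28 = 2 days
- follow-up visit on day +30: 30 − 30 = 0 days
- follow-up visit on day +31 (outside the period), or no follow-up visit, with the last in-period visit on the day of last dose: 30 − 0 = 30 days

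If the patient kept taking drug after the last visit, those on-drug days are added. The planned visit gaps bound them:

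- Up to Week 16, visits are at Weeks 0, 1, 2, 4, 8, 12 and 16 (intervals in Section 6.9.1). The largest gap is 4 × 7 = 28 days.
- After Week 16, assessments are at Weeks 28, 40, 52, 64, 76, 88 and 104 (Section 4.2.3). The gaps are 12 × 7 = 84 days, and (104 − 88) × 7 = 112 days for the last one.

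The upper bounds, if the patient doses through a whole planned gap and has no visit of any kind afterwards, are:

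- up to Week 16: 28 + 30 = 58 days
- after Week 16: 84 + 30 = 114 days, or 112 + 30 = 142 days for the last gap

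**Can one lost event be visible?** Assume about 150 patients per group in the safety population (the planned group size in Section 5). The 2% threshold for common TEAEs (Section 6.14.2.1) is then 3/150 = 2.0%. Losing one patient gives 2/150 = 1.3%, and the term leaves that table unless another group reaches 2%. This illustrates sensitivity and does not estimate how often it would happen.

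**After the change:** if the TEAE window closes at last dose + 30 days, or at the data cut-off if earlier, the uncovered interval is 0 days for every patient.

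**The case against.** The strongest reply is that the practical loss is small and the important events are reported elsewhere. Much of that stands.

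- **The 2-day gap.** The SAP calls 30 days a planned maximum, and the follow-up visit at about 28 days closes a 4-week follow-up period. The 30 days can be read as a tolerance around one visit. The 2 days are therefore a weak argument, and nothing shows that data collected after an attended follow-up visit would be discarded in any number.
- **The long gaps.** The figures of 84 and 112 days require continued dosing followed by no scheduled, unscheduled, early-termination or follow-up visit within the analysis period. The SAP provides for all of these (Sections 6.2.1, 6.2.3 and 6.2). The long gaps also arise only among Week 16 responders at the final lock, where the common-TEAE and special-interest analyses are omitted. In the placebo-controlled period the planned gaps are at most 28 days.
- **Serious events.** A reader might infer that deaths and hospital stays vanish from the report. They do not. The overview counts deaths, SAEs and AE discontinuations without a TEAE condition, the SAE summary covers any SAE, and listings hold all safety data. An AE whose start date is too incomplete to compare is counted as treatment-emergent.
- **Bias between arms.** A reader might also infer a distorted treatment comparison. The SAP gives no basis for saying that the loss differs by arm.
- **Derivation elsewhere.** The SAP does not define the last visit date and refers to compound-level safety standards for several details. A derivation there could shrink the gap.

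None of this reconciles the two rules. Even if the phrase about up to 30 days is read as ending at the last visit, it conflicts with Section 6.14, which includes all data in that window.

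**Conclusion.** The contradiction is real on the text. Both TEAE definitions can exclude an event that Section 6.14 includes in AE tables and that lies inside the analysis period of Section 6.14.2. The consequence is a possible undercount of any-TEAE, severe-TEAE and TEAE-based infection results for patients who do not return. SAE, death, AE-discontinuation and listing outputs are not affected in this way.

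The uncovered time is about 2 days for a patient seen at day 28 and up to 30 off-drug days if there is no later visit, plus any on-drug days since the last visit. The planned gaps of 28 days (to Week 16) and 84 to 112 days (afterwards) are ceilings on that last part, not expected losses. The number of events affected depends on visit attendance and cannot be derived from the SAP. The conclusion assumes that the last visit date means the date of a visit that took place. It is worth correcting because the stated rule gives a wrong count when followed and the change is small.

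**What to change.** In both TEAE definitions of Section 6.14.2, replace the last-visit-date limit with: *on or before the end of the analysis period (30 days after the last dose of study drug including rescue, or the data cut-off if earlier), whether or not a visit took place*. Keeping the reference to rescue holds the window in line with Section 6.14.

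State in a separate sentence that events after the first dose in Study JAIX are attributed to that study. This is an addition: Section 6.14 contains no such cut-off and applies its window regardless of study period. The two must be reconciled explicitly, and the core correction does not depend on it.

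The cost is two sentences of SAP text and one date condition in the TEAE derivation, plus the Study JAIX sentence. TEAE counts may rise slightly.
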